## **Clinical Investigation Plan**

Subjects receiving an MRI as standard of care will receive that benefit irrespective of their participation in this study. The MRI scan may not provide additional benefit for subjects who receive a scan without an underlying medical need.

Any undesirable side effects, under normal conditions of use, are considered acceptable risks when weighed against the performance of the device and benefits to the subject.

### 4.0 STUDY DESIGN

### 4.1 Purpose

The purpose of this study is to confirm the safety of the Prodigy MRI and Proclaim Elite MR conditional SCS systems.

### 4.2 Study design and scope

The study will be performed as an international, multicenter, prospective, and single-arm design. The study will be conducted as a Post Market Clinical Follow Up (PMCF) study and the results will be submitted to the Notified Body: BSI Group (BSI).

The study will be conducted in approximately 20 centers in Europe and up to 10 centers in the US.

### 4.3 Number of subjects required to be included in the study

Approximately forty-nine (49) subjects will be enrolled in the study. Data from only 1 scan per subject will be collected in the study.

### 4.4 Estimated time needed to enroll this subject population

The expected enrollment rate for patients requiring MRIs with an eligible MR conditional device is no more than 10 subjects per year. It is unknown how many patients will be interested in receiving an MRI scan for study purposes without an underlying medical need. Therefore, the number of enrollments per year for this group cannot be predicted with precision. However, we estimate that this number will not be less than the 10 subjects per year that are estimated to require an MRI for medical purposes. Therefore, we estimate that enrollment may continue for up to 6 years.

### 4.5 **Objectives**

### 4.5.1 **Primary objective**

The primary objective of this study is to confirm the safety of the Prodigy MRI and Proclaim Elite MR conditional SCS systems.

### 4.5.2 Secondary objective

The secondary objective is to confirm that the MRI scan does not affect the functionality of the Prodigy MRI or Proclaim Elite MR conditional SCS system.

### 4.6 Endpoints

### 4.6.1 **Primary endpoint**

The primary endpoint is the rate of MRI scan-related adverse events.

### 4.6.2 Secondary endpoint

The secondary endpoints are defined as:

- Rate of successful MRI mode 'turn on/off' functionality
- Rate of successful 'turn on/off' functionality for the stimulation
- Rate of successful adjustments to the program
- Rate of successful interrogations and uploads of the IPG parameters

### 4.7 Inclusion and Exclusion Criteria

A subject, who meets all inclusion criteria and none of the exclusion criteria, is eligible to participate in this study.

All subjects enrolled in the clinical study (including those withdrawn from the clinical study or lost to follow-up) will be accounted for and documented, assigning an identification code linked to their names, alternative identification, or contact information.

This log will be kept up to date throughout the clinical study by the Principal Investigator or his/her authorized designee. To ensure subject privacy and confidentiality of data, this log must be maintained throughout the clinical study at the clinical site.

### 4.7.1 Inclusion criteria

To participate in this clinical study, the subject must meet all the following inclusion criteria:

- Patient has been implanted with a Prodigy MRI or Proclaim Elite MR conditional SCS system
- Patient will receive an MRI scan in compliance with the IFU for the implanted MR conditional SCS system
- Patient is  $\geq 18$  years of age
- Patient must be willing and able to comply with study requirements
- Patient must indicate his/her understanding of the study and willingness to participate by signing an appropriate Informed Consent Form

### 4.7.2 Exclusion criteria

Subjects are not eligible for clinical study participation if they meet any of the following exclusion criteria:

- Patient has another implanted device (active or passive) that prohibits safe scanning
- Patient has previously experienced an MRI scan-related adverse event
- Patient is currently enrolled in another Abbott study that collects MRI safety data
- Patient is incapacitated, is unable to read or write, or is pregnant or breastfeeding

### 4.8 Subject Population

The subject population enrolled in this study will be comprised of male and female subjects from the chronic pain population who have a previously implanted Prodigy MRI or Proclaim Elite MR conditional SCS system.

Subjects will either receive an MRI scan as part of standard of care or will receive an MRI scan without an underlying medical necessity solely for the purposes of this study.

## **Clinical Investigation Plan**

Subjects must meet the specific eligibility criteria and provide informed consent to participate in the study.

### 4.8.1 Subject screening

All subjects presenting at the investigational site can be screened by a member of the investigational team previously trained on the CIP and delegated to do so.

Subjects who do not meet the inclusion/exclusion criteria will not be eligible to participate in this study. Subjects meeting the inclusion criteria and none of the exclusion criteria will be fully informed about the study and asked to participate in the study.

In case the subject agrees, a duly signed and dated Informed Consent form will be obtained. Once enrolled, the subject is expected to comply with the scheduled visits and required activities according to the protocol.

### 4.8.2 Point of enrollment

A subject is enrolled in this study only when he/she has provided a written signed and dated Informed Consent form.

### 4.8.3 Vulnerable population

Not applicable.

### 4.9 Informed Consent Process

### 4.9.1 General process

The Investigator or his/her authorized designee (if applicable) will conduct the Informed Consent process, as required by applicable regulations and the center's IRB/EC. This process will include a verbal discussion with the subject on all aspects of the clinical investigation that are relevant to the subject's decision to participate, such as details of clinical investigation procedures, anticipated benefits, and potential risks of clinical investigation participation. Subjects must be informed about their right to withdraw from the clinical investigation at any time and for any reason without sanction, penalty or loss of benefits to which the subject is otherwise entitled. Withdrawal from the clinical investigation will not jeopardize their future medical care or relationship with the investigator.

During the discussion, the Principal Investigator or his/her authorized designee will avoid any improper influence on the subject and will respect subject's legal rights. Financial incentives will not be given to the subject. Subjects may be compensated for time and travel directly related to the participation in the clinical investigation. The subject shall be provided with the Informed Consent form written in a language that is understandable to the subject and has been approved by the center's IRB/EC. The subject shall have adequate time to review, ask questions, and consider participation. The Principal Investigator or his/her authorized designee will make efforts to ensure that the subject understands the information provided. If the subject agrees to participate, the Informed Consent form must be signed and dated by the subject and thereafter by the person obtaining the consent prior to any clinical investigation-specific procedures. The signed original will be filed in the subject's hospital or research charts, and a copy will be provided to the subject.

# **Clinical Investigation Plan**

Failure to obtain informed consent from a subject prior to clinical investigation enrollment should be reported to Sponsor within 5 working days and to the reviewing center's IRB/EC according to the IRB's/ EC's reporting requirements.

If, during the clinical investigation, new information becomes available that can significantly affect a subject's future health and medical care, the Principal Investigator or his/her authorized designee (if applicable) will provide this information to the subject. If relevant, the subject will be asked to confirm their continuing informed consent in writing.

### 4.9.1.1 Special Circumstances for Informed Consent

Incapacitated individuals, defined as persons who are mentally ill, mentally handicapped, or individuals without legal authority are excluded from the study population. Individuals under the age of 18 or age of legal consent are excluded from the study population. Individuals unable to read or write are excluded from the study population. Pregnant or breastfeeding women are excluded from the study population.

In addition, an authorization for use and disclosure of the subject's protected health information, in accordance with the Health Insurance Portability and Accountability Act (HIPAA), must be obtained from the subject or their legally acceptable representative.

### 5.0 STUDY DEVICE

### 5.1 Name of study devices

Any market-released, Prodigy MRI or Proclaim Elite MR conditional SCS system may be used in this study along with its relevant accessories. Table 1 includes a list of all devices included in this study.

Device name	Model/Type	Serial/Lot Controlled	Manufacturer	Region/ Country	Investigational or Market Released
Proclaim Elite Implantable Pulse Generator	3660 & 3662	Serialized	St. Jude Medical	Global	Market Released
Prodigy MRI Implantable Pulse Generator	3772	Serialized	St. Jude Medical	Global	Market Released
Octrode™ Lead	3186	Serialized/Lot	St. Jude Medical	Global	Market Released
Penta™ Lead	3228	Serialized/Lot	St. Jude Medical	Global	Market Released
Butterfly Anchor	1105	Lot	St. Jude Medical	Global	Market Released

Table 1. Study Devices

# **Clinical Investigation Plan**

Device name	Model/Type	Serial/Lot Controlled	Manufacturer	Region/ Country	Investigational or Market Released
Long Anchor	1106	Lot	St. Jude Medical	Global	Market Released
Swift-Lock TM Anchor	1192	Lot	St. Jude Medical	Global	Market Released
Cinch TM Anchor	1194	Lot	St. Jude Medical	Global	Market Released
Prodigy Charging System	3730	Serialized	St. Jude Medical	Global	Market Released
Prodigy Patient Programmer	3856	Serialized	St. Jude Medical	Global	Market Released
Rapid Programmer ™ System	3835	Serialized	St. Jude Medical	Global	Market Released
Clinician Programmer	3872	Serialized	St. Jude Medical	Global	Market Released
Patient Controller	3883	Serialized	St. Jude Medical	Global	Market Released

Note: Changes to the lead manufacturing process means that some existing leads may have been lot controlled while others were serialized.

### 5.2 Indication for Use

The Prodigy MRI and Proclaim Elite SCS systems are indicated as an aid in the management of chronic, intractable pain of the trunk and/or limbs, including unilateral or bilateral pain associated with the following: failed back surgery syndrome and intractable low back and leg pain.

### **5.3** Description of the study devices

Please refer to the country- and device-specific IFU for additional information regarding the devices used in this clinical investigation.

The Proclaim Elite system is MR conditional for scans of the head, extremities (upper except shoulder, lower except hip), or any other body part. The Prodigy MRI system is only MR conditional for scans of the head and extremities (upper except shoulder, lower except hip). Scan requirements for each system (Proclaim Elite and Prodigy MRI)/lead (Octrode and Penta) combination are provided in the MRI Procedure Information Manual.

Clinically relevant MRI safety criteria identified by St. Jude Medical (now Abbott) are unchanged between the Prodigy MRI and Proclaim Elite systems. Additional Proof of Safety testing has demonstrated that the Proclaim Elite device satisfies these same criteria when used with a body RF

## **Clinical Investigation Plan**

transmit coil under the specified scan conditions. Therefore, data gathered on Proclaim Elite and Prodigy MRI will be evaluated as a single group.

### 5.4 MRI Procedure Information Manual

To ensure the MR Conditional requirements are met, the healthcare providers involved in MRI scanning of the Prodigy MRI and Proclaim SCS systems will need to take multiple actions. To ensure subject and device safety during the MRI procedure, a recommended procedural workflow has been developed in the MRI Procedure Information manual. To collect impedance check data in this study, this clinical investigation plan adds the requirement of having a Clinician Programmer (for Proclaim devices) or a Rapid Programmer (for Prodigy devices) present at every MRI scan.

The MRI Procedure Information manual allows for the determination of whether conditions have been satisfied by the SCS system and the MR environment to qualify for an MRI scan. This labeling allows radiologists and MR technologists to identify MR conditional components and assess whether their MRI equipment can safely scan a subject implanted with an Abbott (formerly St. Jude Medical) MR conditional SCS system. Guidance is also provided to the physician and subject on how to prepare for an MRI scan.

Additionally, a Subject Identification (ID) Card is provided to all subjects as labeling that allows for identification of their implanted neurostimulation system in support of determining if the subject has an MR conditional system.

Additional resources (including the MRI Procedure Information manual) for ensuring that the MRI scan complies with the MRI conditional labeling can be obtained from the Sponsor or found on the following websites:

- https://www.sjm.com/en/professionals/resources-and-reimbursement/technical-resources/mri-ready-resources
- https://manuals.sjm.com/

### 5.5 Device handling & storage

The Sponsor requires all products to be stored according to the appropriate labeling and IFU as per standard practice at each center.

### 6.0 PROCEDURES

### 6.1 Study flow chart

### 6.2 Procedures

The clinical study will be conducted in accordance with the CIP. All parties participating in the conduct of the clinical study will be qualified by education, training, or experience to perform their tasks and this training will be documented appropriately.

The clinical study will not commence until Abbott receives written approval from the IRB/EC and relevant regulatory authorities and all required documents have been collected from the site(s).

	ay speeme		10000aures			
Visit Study Activity	Enrollment (in clinic, prior to MRI scan)	Baseline (in clinic, prior to MRI scan)	MRI scan (in clinic, pre-, during, and post-scan	1 Month follow up (in clinic, 1 months ± 10 days since MRI scan)	Unscheduled	Additional surgery
Informed Consent Process	Х					

### Table 2: List of all study specific activities/procedures

SJM-CIP-10056

Page 18 of 49

This confidential document is the property of Abbott and shall not be reproduced, distributed, disclosed or used without the express written consent of Abbott

## **Clinical Investigation Plan**

Visit Study Activity	Enrollment (in clinic, prior to MRI scan)	Baseline (in clinic, prior to MRI scan)	MRI scan (in clinic, pre-, during, and post-scan	1 Month follow up (in clinic, 1 months ± 10 days since MRI scan)	Unscheduled	Additional surgery
Inclusion/Exclusion Criteria Check	Х					
Demographics Collection		Х				
Collection of Medical Condition indicated for MRI scan		Х				
Subject eligibility for MRI scan Check			X (pre- scan)			
Lead and IPG data Collection		Х				Х
Programming Functionality			X (pre- and post-scan)	Х	Х	
Device Functionality Check			X (pre-and post-scan)			
MRI Scan			X			
MRI Scan Parameters Collection			Х			
Determine Reason for the Visit and Action Taken					Х	Х
Adverse Events Check		(X)	(X)	(X)	(X)	(X)
Protocol Deviation	(X)	(X)	(X)	(X)	(X)	(X)

(X) if applicable

### Informed Consent Procedure and Inclusion/Exclusion Criteria:

Subject's eligibility criteria and Informed Consent Procedure is performed at the Enrollment visit.

### **Demographics:**

Subject's year of birth, weight, height, and sex will be collected at the Baseline visit.

### Medical Condition indicated for MRI Scan:

Subject's medical condition requiring a MRI scan will be collected at the Baseline visit.

### Subject's eligibility for MRI scan:

Subject's eligibility for MRI scan will be checked BEFORE the scan will be done.

### Lead, Extension, Anchor and IPG Data:

At Baseline, and in case of additional surgery, information of the implanted leads and IPG (model number, serial/lot number, and positions), presence and type of any anchors used, as well as the presence of lead extensions, will be collected.

### **Programming Functionality:**

## **Clinical Investigation Plan**

Information regarding the ability to re-program will be collected at pre- and post-scan, during the 1-month follow up visit and at unscheduled visits.

### **Device Functionality:**

Data regarding the device functionality, including impedance check, will be collected pre-and postscan.

### MRI Scan:

MRI scan will be conducted in compliance with the SJM Instructions for Use (IFU) for the implanted MR conditional SCS system and the MRI Procedure Information manual.

### **MRI Scan Parameters:**

MRI scan parameters will be documented post-scan.

### Reason for the Visit and Action taken:

Information regarding the reason for the visit, as well the action taken, will be collected in case of unscheduled visit or additional surgery.

Adverse Events Check: Serious adverse events (SAEs) and/or MRI scan-related adverse events will be checked at all visits except enrollment.

### 6.3 Enrollment visit

(In clinic, prior to performing MRI scan)

The following activities are performed after the subject has been screened and must occur before any procedure/visit.

- The principal or delegated Investigator is responsible for screening all potential subjects to determine subject eligibility for the study
- If a subject meets all inclusion criteria and does not meet any of the exclusion criteria, he/she is eligible for the study
- The subject is enrolled in the study when the subject signed the EC approved consent form

Enrollment information (name of the study, date of consent and inclusion/exclusion information) will be recorded in the hospital records the Enrollment form will be completed, preferably within 5 days after enrollment.

As soon as the subject signs the Informed Consent Form, AEs need to be reported according to the guidelines mentioned in this CIP.

In case the subject was consented to participate in the study, but does not meet inclusion/exclusion criteria, and did not receive a MRI scan, the subject should be withdrawn and a Withdrawal form must be completed. The subject will resume his/her regular standard of care with his/her physician.

In case the subject was consented to participate in the study and did receive a MRI scan, but does not meet inclusion/exclusion criteria, it will be considered a protocol violation. A protocol deviation form needs to be completed and the Sponsor must be informed. The EC and Competent Authority

# **Clinical Investigation Plan**

(CA), if applicable, should be notified appropriately about any deviations with regards to the violation of inclusion/exclusion criteria.

### 6.4 Baseline visit

(In clinic, prior to performing MRI scan) The baseline visit may be conducted on the same day as -but prior to- the MRI scan.

The following information will be collected at the baseline visit:

- Demographics
- Medical condition indicated for an MRI scan
- Lead and IPG data
- AE and/or protocol deviation (if applicable)

### 6.5 MRI scan

(In clinic)

There is no minimum required time gap between implantation of the neurostimulator and the MRI scan. This will be determined by the physician's standard of care.

### 6.5.1 Pre-scan

- Subject eligibility for MRI scan
- Device functionality, including impedance check
- Programming functionality
- AE and/or protocol deviation (if applicable)

MRI scan will be performed. Ensure to follow the instructions as mentioned in the MRI Procedure manual.

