### 12.8 Procedures that take into account all the data

All subjects who have signed an Informed Consent will be considered enrolled in the clinical investigation (refer to Section 4.8.2). However, it is anticipated that there will be subjects who are enrolled in the study but will not be included in the primary endpoint analysis, such as:

- Subjects who are enrolled but do not meet baseline inclusion or meet exclusion criteria before the MRI scan; these are considered as screen failures
- Subjects who are enrolled but do not receive a MRI scan

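### Inclusion/exclusion criteria are scheduled for checking only at Enrollment, the pre-scan eligibility check is undefined, and section 12.8 does not fix screen-failure status before the scan

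*Combined protocol and SAP*

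**What the plan says.** **Timing of the criteria check.** Table 2 has a row "Inclusion/Exclusion Criteria Check" with a mark under Enrollment and nowhere else. The text of section 6.2 agrees: "Subject's eligibility criteria and Informed Consent Procedure is performed at the Enrollment visit". Neither the Baseline list (6.4) nor the pre-scan list (6.5.1) includes it.

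**Interval to the scan.** Enrollment need only be "In clinic, prior to performing MRI scan" (6.3). For Baseline, "The baseline visit may be conducted on the same day as -but prior to- the MRI scan" (6.4), so the same day is allowed but not required. No upper limit is given for either interval.

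**The pre-scan check.** Section 6.5.1 lists "Subject eligibility for MRI scan" as a single line, and Table 2 gives it its own row. Section 6.2 adds only that it comes before the scan. The nearest description of what qualifies a scan is in section 5.4, on the MRI Procedure Information Manual, which "allows for the determination of whether conditions have been satisfied by the SCS system and the MR environment to qualify for an MRI scan".

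**Who may be scanned.** Section 4.8 admits subjects whose scan has no medical indication and is done only for the study. Section 4.7.2 lists the exclusions, and section 4.9.1.1 restates one of them: "Pregnant or breastfeeding women are excluded from the study population".

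**What follows from ineligibility.** Under section 6.3, a consented, ineligible subject who has not been scanned is withdrawn; if that subject has been scanned, it is a protocol violation. Section 12.8 gives examples of enrolled subjects left out of the primary endpoint analysis. The first is "Subjects who are enrolled but do not meet baseline inclusion or meet exclusion criteria before the MRI scan; these are considered as screen failures". A second, separate example covers those who receive no scan.

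**The concern.** Several exclusions describe a state that can change after consent. If the criteria are looked at once, at an unlimited distance from the scan, the subject's status on the scan day rests on a check whose content the CIP does not give. Section 3.6 accepts that a scan without medical need may bring the subject no benefit, and no clinical referral stands behind such a scan as a second safeguard. Section 7.2 itself says that failing to adhere to these criteria may count as failing to protect subjects.

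The second stake is the primary analysis. Section 12.8 turns on whether a subject met an exclusion before the MRI, but the CIP names no record that fixes this at that time. If the question is settled later, membership of the primary safety analysis could be decided with the adverse-event outcome already known.

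**Working it through.** **Step 1: what each scheduled step covers.**

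| Step | Content stated in the CIP | Are the 4.7 criteria re-checked? |
|---|---|---|
| Enrollment (6.3, Table 2) | Consent, inclusion/exclusion | Checked here |
| Baseline (6.4) | Demographics, MRI indication, lead and IPG data, AEs and deviations | No |
| Pre-scan (6.5.1) | MRI-scan eligibility (undefined), device and programming functionality, AEs and deviations | Not stated |

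**Step 2: which exclusions can change, and what might catch the change.**

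- Pregnancy or breastfeeding: no step stated in the CIP is shown to detect it.
- A new implant that rules out safe scanning: the scan must follow the IFU and the manual (4.7.1, 6.2), which may catch it. The manual is under separate cover (Appendix E), so this cannot be confirmed.
- Entry into another Abbott MRI study: this is a study criterion, and nothing shows that a device manual would capture it.
- An MRI scan-related event at an interim scan: largely covered. AE reporting starts at consent (6.3, 8.2), and AEs are checked at Baseline and at the scan visit (6.2, 6.4, 6.5.1).

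**Step 3: is the interval real?** Section 12.2 allows about 5% dropout between enrollment and the scan visit, so the plan does not treat the two as one event. Its length is not given, so the number of subjects whose status changes cannot be estimated.

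**Step 4: section 6.3 beside section 12.8.** Unscanned subjects have their own example in 12.8, so the screen-failure example can be read to reach a scanned subject. Section 6.3 calls that same subject a protocol violation and does not say whether the subject is analysed. The examples in 12.8 are introduced as illustrations, not a closed list.

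**Step 5: sensitivity of the test to one subject's membership.** Inputs from 12.1 and 12.2: performance goal 10%, assumed rate 1%, one-sided 5%, Clopper-Pearson bound, n = 46, 5% dropout.

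The plan's own figures come first. The upper bound for x subjects with an event lies below 0.10 exactly when P(X ≤ x | n, 0.10) < 0.05.

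- n = 46, x = 1: 0.9^46 + 46 × 0.1 × 0.9^45 = 0.0480, so one event is allowed (upper bound 9.9%).
- Power at 1%: 0.99^46 + 46 × 0.01 × 0.99^45 = 0.9225. This meets the stated 80%, and 46 is the smallest n that does.
- 46/0.95 = 48.4, rounded up to 49.

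The stated 46 and 49 therefore reproduce. With one analysed subject fewer:

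- n = 45, x = 1: 0.9^45 + 45 × 0.1 × 0.9^44 = 0.0524, so one event fails (upper bound 10.1%) and none is allowed.
- Power at 1%: 0.99^45 = 0.636.

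Membership can also work the other way. At n = 47 the allowed number is still 1, so 2 events in 47 fail. Leaving out one of the two subjects with an event gives 1 in 46, which passes.

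**The case against.** The strongest reply is that the CIP already has a check called subject eligibility immediately before the scan. A reader might infer from section 5.4 that this check is confined to the stimulation system and the MR environment. The documents do not support that: 5.4 describes what the manual makes it possible to determine, not the content of the check, and the manual and CRFs (Appendices E and H) are not in the documents. The check may cover pregnancy or other implants. This part of the reply stands; what remains is that the CIP neither defines the check nor says that it repeats section 4.7.2.

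A reader might also infer that the plan lets an ineligible subject be scanned. It does not. Section 6.3 requires a deviation form and notice to the sponsor, with appropriate notification of the ethics committee and, if applicable, the competent authority. Section 6.14 lists failure to meet the criteria as a reason for withdrawal. But these provisions act once ineligibility is known, and a violation recorded afterwards does not protect the subject. Entry into another Abbott study is also not evidently a protective exclusion.

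On the analysis, section 12.8 can be read together with 6.3 as meaning unscanned subjects only, in which case nobody is removed after a scan. That reading is possible, but the separate example for unscanned subjects does not compel it. Finally, a fall from 46 to 45 is not predicted by anything in the plan: about 49 are to be enrolled, and the synopsis ends the study at data from 46 scanned subjects, so a removal may be absorbed.

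**Conclusion.** The concern holds as a gap in detection and in the analysis rule. The visit schedule can be followed in full without any stated step shown to find a change after consent, above all in pregnancy or breastfeeding, and also a new implant or entry into another Abbott MRI study. Separately, sections 6.3 and 12.8 do not settle whether a scanned subject later found ineligible is analysed, and this leaves room for that choice to follow the outcome.

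The number of subjects affected is unknown and is not estimated here. The bounds of 9.9% and 10.1% show how much can turn on one subject's membership; they are not an expected loss. The conclusion rests on the CIP text alone. If the manual or the CRFs repeat the section 4.7 criteria before the scan with a date, the detection gap largely closes and only the wording of 6.3 and 12.8 remains to be reconciled. This is a worthwhile, inexpensive improvement and does not show that the design is unsound.

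**What to change.** 1. In Table 2 and section 6.5.1, add a dated re-confirmation by the investigator, before the scan starts, that the existing section 4.7 criteria are still met. If the present pre-scan eligibility check is meant to include this, define it and say so. No new criterion is needed.
2. In section 12.8, state that screen-failure status is fixed by that record before the scan and cannot be reassigned afterwards. A scanned subject then stays in the primary analysis, and any ineligibility found later is reported as a deviation. Align section 6.3 with this wording.

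Cost: one section on the pre-scan CRF and edits to Table 2, 6.3, 6.5.1 and 12.8, with no added visit or test. The downside is that a few enrolled subjects may be withdrawn before the scan and have to be replaced, adding to the dropout for which 12.2 allows about 5%.
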